3. STUDY DEVICE NAME AND DESCRIPTION

3.1. Study Device Name: Skin Tag Remover (STR)

For this Protocol, the study device will be referred to as "Skin Tag Removal" study device or "STR" study device. There are two versions of the STR study device, automatic and manual. Each version is also manufactured in two sizes which correspond to the size of the skin tag to be removed.

Under protocol version 1, t he smaller size (to be referred to as "micro" for the remainder of this document) is designed to be used with skin tags having a base measuring between 2–4mm. The larger size (to be referred to as "standard" for the remainder of the document) is to be used with tags having a base measuring between 4–6 mm.

Under protocol version 2, the micro size band will be used on all skin tags measuring between 4-6mm. The standard size will no longer be used and skin tags measuring between 2-4mm will not be enrolled.

Product labeling has a helpful guide for determining size of band to use. All four versions function in the same manner by placing a band at the base of the skin tag, therefore, this document will collectively refer to all four iterations of the study device as "STR."

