3.2. General Description of Study Device

The STR study devices are designed for the removal of skin tags from the body by ligation of the blood supply to the skin tag through the application of a small elastic band. Bands are placed around the base of the skin tag by using an applicator, which pushes the band from a cylindrical extension on the device over the skin tag and to the base of the tag.

The study device(s) are available in two different sizes to ensure the bands being used are tight enough to restrict the blood supply for skin tags that vary in size⁴.

- Under protocol version 1: The micro version of the STR study device has been designed to remove skin tags that measure 2-4mm at the base, and the standard version is designed to remove skin tags that measure 4-6mm at their base. When determining band size, it is suggested to use the smaller (micro) device for tags that are in-between micro and standard for best results.
- Under protocol version 2: The micro size will be used on skin tags that measure 4-6mm at their base. The standard size will not be used. Additional Skin tags measuring 2-4mm will not be enrolled.

_

⁴ Image from product's UK labeling

For general information about this device, currently sold in the UK, please reference https://tagband.co.uk.

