6.1. Purpose and Study Arms

This pivotal investigational study is designed to evaluate the safety and efficacy of a skin tag removal (STR) study device. This is a non-significant risk interventional clinical study that will be conducted by a Clinical Research Organization (CRO) with a licensed dermatologist(s) to serve as Principal Investigator. There are two arms of the study that are only differentiated by the type of STR study device used; arm 1 will be conducted using the manual version, and arm 2 will use the automatic version.

After consultation with the FDA, the Sponsor has modified the original protocol to include the following changes:

- Exclusion of all skin tags located around the eye, on the eyelid, or the groin area (6.2.1)
- Clarification of covered medical expenses while enrolled in the study (6.2.4)
- Protocol includes updated exclusion conditions (excluding those with known hypertrophic scarring or keloid scarring)
- Protocol includes the addition of an electronic daily diary for all participants
- A study was conducted to power the investigation for biostatistical relevance properly (please see the report in the Reference section). The conditions for power analysis were:
 - The primary endpoint is the removal of the skin tag (effectiveness)
 - The observed percentage of successful removal is 60%; i.e. 60% of the skin tags treated are expected to be successfully removed with use of the device
 - A 95% Confidence Interval (CI) was used to determine the number of subjects necessary for participation

Determination: if a successful clinical trial is established at 60% of treated skin tags removed, a study powered with 200 treated tags will have a 95% confidence interval of 5.5%

The power analysis determined that the sponsor should enroll enough subjects to treat a total of 200 skin tags. Typically, patients seeking skin tag removal have from 1 to 5 tags that could be treated for removal, however, for this study, only a maximum of 2 tags per person will be treated. Therefore, the number of tags for intention to treat (ITT) in each arm is 100 for a study total of 200 tags. This approach will ensure that the study has been powered to a 95% confidence interval of 5.5%.

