Approximately two thirds of the subjects in each arm are to receive micro bands (2-6 mm skin tags treated), while the other one third is to receive standard size bands (4-6mm size skin tags treated). The PI will manage the number of treated skin tags such that a variety of locations on the body (face, neck, arms, and torso) are represented in the study.

Under Protocol Version 1:

Arms	Assigned Interventions
Arm 1 – Manual Version Goal: successful removal of 60% of the skin tags treated with the STR device. Subjects will have up to two (2) tags treated, therefore, 50–100 subjects are anticipated for this arm. A total of 100 skin tags is the ITT (intention to treat).	Subject treatment data collected on: • Band size; 2-4mm (micro), or 4-6mm (standard) • Subject pool divided ~equally by band size • All skin tags will be banded by a healthcare professional
Arm 2 – Auto Version Goal: successful removal of 60% of the skin tags treated with the STR device. Subjects will have up to two (2) tags treated, therefore, 50-100 subjects are anticipated for this arm. A total of 100 skin tags is the ITT (intention to treat).	Subject treatment data collected on: • Band size; 2-4mm (micro), or 4-6mm (standard) • Subject pool divided ~equally by band size • All skin tags will be banded by a healthcare professional

Under Protocol Version 2:

Arms	Assigned Interventions
Arm 1 – Manual Version Goal: successful removal of 60% of the skin tags treated with the STR device. Subjects will have up to two (2) tags treated, therefore, 50–100 subjects are anticipated for this arm. A total of 100 skin tags is the ITT (intention to treat).	Subject treatment data collected on: Tag size; 4-6 mm (micro band) All skin tags will be banded by a healthcare professional

Arm 2 - Auto Version

Goal: successful removal of 60% of the skin tags treated with the STR device. Subjects will have up to two (2) tags treated, therefore, 50-100 subjects are anticipated for this arm. A total of 100 skin tags is the ITT (intention to treat).

Subject treatment data collected on:

- Tag size; 4-6 mm (micro band)
- All skin tags will be banded by a healthcare professional licensed dermatologist

For subjects meeting the inclusion/exclusion criteria and entering the study and having two skin tags being treated as a part of this study, please see the study design details on how both skin tags are to be treated in Section 6.2 below.

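### The band mix in section 6.1 fits neither protocol version, only a pool of both: reconcile the make-up of the 200 tags, and report removal by version if they are pooled

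*Protocol*

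**What the plan says.** Section 6.1 gives a band mix above both version tables and names no version: "Approximately two thirds of the subjects in each arm are to receive micro bands (2-6 mm skin tags treated"). The rest of the sentence assigns the larger band, for 4-6 mm tags, to everyone else: "the other one third is to receive standard size bands".

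The version-specific text says otherwise:

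- **Version 1.** The arm table has "Subject pool divided ~equally by band size". Section 6.2.1 agrees and ties micro to 2-4 mm and standard to 4-6 mm.
- **Version 2.** The arm table has "Tag size; 4-6 mm (micro band"). Section 3.1 adds: "The standard size will no longer be used and skin tags measuring between 2-4mm will not be enrolled". Section 3.2 words it slightly differently: "Additional Skin tags measuring 2-4mm will not be enrolled".

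On the total, section 6.1 says "Therefore, the number of tags for intention to treat (ITT) in each arm is 100 for a study total of 200 tags". Both version tables repeat, for each arm, "A total of 100 skin tags is the ITT (intention to treat") and the same 60% goal.

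On reporting, section 6.2.6.1 gives the number of tags treated and removed, breaks the rate down by tag size with micro and standard as the two categories, and lists micro against standard band as a subgroup. The Visit 1 entry in section 6.2.6 records size in the same two words. Section 2.2 sets the endpoint as removal within 20 days.

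The change table at the front describes the conditions of Version 1 tags: diaries to Day 10, no bandage, and no rebanding, with withdrawal if the band came off early. Version 2 has diaries to Day 20, a bandage and up to two rebandings per tag. The same table describes the Version 2 schematic in section 6.2.1 as showing a 3:1 micro-to-standard ratio.

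**The concern.** The band-mix sentence determines which tags make up the 200, and so what the removal rate and the 60% goal describe. Read as a plan for either version alone, it is wrong. Read as a cumulative mix, it means that most or half of the 200 tags come from Version 1.

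Three things follow on the pooled reading:

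- A single rate combines tags with different band fit, bandaging, rebanding rules and diary length, although the endpoint runs to Day 20.
- Band size is confounded with version, because every standard band is a Version 1 band. The micro-against-standard subgroup cannot separate the two.
- The Version 2 conditions rest on far fewer than 200 tags, and no precision is stated for that number.

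If Version 1 tags do not count, then the band-mix sentence and the band-size subgroup are both obsolete.

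The size categories are a related problem. Once micro bands go on 4-6 mm tags, the words micro and standard no longer name a tag size.

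**Working it through.** **Does the sentence fit either version?**

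| Source | Micro share | Tag size under micro band |
|---|---|---|
| Section 6.1, unlabelled sentence | about 67% | 2-6 mm |
| Version 1 (6.1 table, 6.2.1) | about 50% | 2-4 mm |
| Version 2 (3.1, 3.2, 6.1 table, 6.2.1) | 100% | 4-6 mm |

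It fits neither on share or on size. The 2-6 mm range is the union of the two version ranges, which is what a pool would give.

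**The plan's own precision figure.** Section 6.1 states 5.5% for 200 tags at 60%. The normal-approximation half-width is 1.96 × √(0.60 × 0.40 / 200) = 6.8 points, so 5.5 is not reproduced at 60%. It is reproduced at 80%: 1.96 × √(0.80 × 0.20 / 200) = 5.5. That mismatch is a separate matter; 6.8 is the reference below.

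**Tags per version implied by pooling 200.** Assume that Version 1 was split exactly 1:1 by band, that tags per subject do not differ between bands (the sentence counts subjects), and that all standard bands are Version 1. Version 1 tags are then twice the standard-band tags.

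- 2:1 mix (section 6.1): standard = 200/3 = 67; Version 1 = 133; Version 2 = 67.
- 3:1 mix (change table): standard = 200/4 = 50; Version 1 = 100; Version 2 = 100.

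**95% half-width for the Version 2 rate at 60%**, 1.96 × √(0.24/n), ignoring clustering of two tags in one subject:

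| Composition of the 200 | Version 2 tags | Half-width, overall | Half-width, per arm |
|---|---|---|---|
| All Version 2 | 200 | 6.8 points | 9.6 points (n = 100) |
| Pooled, 3:1 | 100 | 9.6 points | 13.6 points (n = 50) |
| Pooled, 2:1 | 67 | 11.8 points | 16.6 points (n = 33) |

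**Shift of the pooled rate.** Pooled rate minus Version 2 rate = (Version 1 share) × (Version 1 rate − Version 2 rate). With shares of 0.667 and 0.50, each 10-point difference between versions moves the pooled rate 6.7 points (2:1) or 5.0 points (3:1). The protocol gives no Version 1 rate, so neither the sign nor the size of the actual shift can be worked out.

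**Size categories on the pooled reading.**

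- Read by band: 2-4 mm tags make up 67/133 = 50% (2:1) or 50/150 = 33% (3:1) of the micro row.
- Read by millimetres: standard bands make up 67/133 = 50% or 50/150 = 33% of the 4-6 mm row.

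**The case against.** The best reply is that the text already points to one cumulative total. Section 6.1 speaks of a study total. Section 3.2 bars only additional 2-4 mm tags. Section 6.2.6.1 reports all treated tags and keeps a standard-band category that only Version 1 tags can fill. The 100-tag and 60% entries are identical in both version tables, so they look like arm-level targets repeated, not separate targets for each version. On this view the sentence lacks a label and little more.

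Much of this stands. A reader might infer that the protocol is wholly silent on pooling, or that the two tables add up to 400 tags. The documents support neither: the text leans toward pooling, and sections 6.1 and 6.2.1 fix the total at 200. The section 6.2.1 figures are not shown and may carry the split, so nothing is inferred from their absence.

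What does not fall away is the conflict in the visible text. The Version 2 table assigns its full 100 tags per arm to micro bands on 4-6 mm tags, which a one-third share of standard bands contradicts, and the 2:1 mix differs from the 3:1 of the change table.

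It can also be said that pooling rules belong in the statistical analysis plan. That plan may well define the analysis sets. It would not correct a protocol sentence that misstates who makes up the 200, or size categories that no longer describe size.

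Finally, tag diameter is recorded (section 6.2.3) and band size is a separate subgroup, so no data are lost. That is true, and it is why the remedy is cheap.

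**Conclusion.** The point holds as a conflict to be reconciled. The section 6.1 sentence matches neither version and is coherent only as a pool of both. Other sections lean toward that pool; the Version 2 arm table does not fit it. On the pooled reading, the Version 2 result rests on about 67 or 100 tags, with a half-width at 60% of about 11.8 or 9.6 points instead of 6.8. These figures assume a 1:1 Version 1 split and equal tags per subject, and they ignore clustering.

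Two stronger conclusions are tempting and not supported. One is that Version 1 tags would pull the result down. The change table says only that Version 1 did not reach the desired level, and with no rate given the direction is unknown. The other is that Version 2 tags must be the sole primary set. That is one option; the documents do not require it, and it would remove treated tags from the primary result after a recorded shortfall.

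Conduct under Version 2 is clear. The problem is the base of the primary result, its precision, and the size categories. It should be fixed, but it is not fatal.

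**What to change.** - In section 6.1, label the two-thirds/one-third sentence as the cumulative mix across versions, or reconcile it with the Version 2 text.
- State, before results are reviewed, whether the 200 tags and the 60% goal include Version 1 tags.
- If they do, report the removal rate with its 95% interval by protocol version, add protocol version to the subgroups in section 6.2.6.1, and state the expected precision for the Version 2 tags, overall and per arm. If they do not, remove the sentence and the micro-against-standard subgroup.
- In sections 6.2.6 and 6.2.6.1, report tag size as measured base diameter in mm, separately from band size.

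The cost is protocol wording, one subgroup line and one extra table. No new data are needed, because diameter is already recorded. The real downside is that, if the versions are pooled, the Version 2 result is shown with a wider interval than the pooled one. No choice of primary set is imposed.

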6.2. Study Design

This protocol was developed after consultation with the FDA under a Q-submission, Q222756, where it was determined to be a non-significant risk trial.

6.2.1. Recruitment Population

For both arms of the study, subjects located in the U.S. will be recruited from the general population and/or through an invitation presented by the Principal Investigator or CRO. Potential participants may self-complete an IRB-approved online pre-screening survey. Every effort will be made to recruit well-represented subjects from the following groups:

- Age (22-50 and 51+)
- Sex assigned at birth (M/F)
- Race/Ethnicity
- Fitzpatrick Skin Type

The study cohort target is between 30 and 70 subjects per arm (depending on how many skin tags each subject presents for treatment), as determined by the power analysis.

Under Protocol Version 1, the study included two arms (manual and automatic STR application), and participants were treated with either the micro (2–4mm) or standard (4–6mm) sized band depending on the measured base width of the skin tag. Each arm included a roughly equal number of tags treated with each device size.

It is anticipated that some subjects will likely have several skin tags that could be treated with the STR study device. A maximum of two skin tags per subject may be chosen for treatment. For purposes of pooling the data more effectively, if a subject opts to have two skin tags treated in the study, the

following must apply;

- both skin tags must be of the same size; either micro (2-4mm); or standard (4-6mm).
 U nder protocol version 2, only skin tags measuring between 4-6mm will be banded with the micro size.
- both skin tags must be treated in the same arm (e.g. using the same STR study device, manual or automatic)
- skin tags must be in two different, distinguishable locations on the body (i.e. right side of neck and left armpit)

As of Protocol Version 2, only skin tags measuring 4–6mm at the base will be eligible for enrollment, and only the micro version of the STR device will be used. The standard-sized band will no longer be used in this version of the study. Participants may still have up to two eligible skin tags treated, provided both are within the 4–6mm size range, in different anatomical locations, and treated using the same device arm (manual or automatic).

Participants previously enrolled under an earlier version of the protocol may be eligible to reenroll, provided a different, previously unbanded skin tag(s) is selected for treatment. Skin tags previously banded are not eligible for rebanding under this protocol version.

Therefore, the total intention to treat (ITT) is 200 skin tags for arms 1 and 2 combined. If the study is completed with subjects only having one skin tag treated, then the study would need to recruit 200 subjects. If each subject had two skin tags treated, only 100 subjects would need to be recruited. It is anticipated that between 100 and 200 subjects will be required to treat a total of 200 skin tags.

The figures below depict how the total subject pool would be divided into the two arms under both versions of the protocol, where "N" is the number of subjects:

Under Protocol Version 1: Figure 1

[figure not shown]

Figure 1: Breakdown of subjects into each arm and size of band used to be stratified as equally as possible in the targeting of ~200 treated skin tags.

[figure not shown]

Figure 2: Breakdown of subjects into each arm to be stratified as equally as possible in the targeting of ~200 treated skin tags.

Once enrolled in the study, the Investigator will assign an STR version for use (manual/ automatic . Only the micro-sized band will be used in this version of the protocol, and only skin tags measuring 4–6mm at the base will be eligible for treatment. The Investigator will also review the subject's skin tags and agree with the subject on the body location and skin tag(s) that will be treated (see exclusion criteria) . The Investigator will also verify that the skin tag does not present a morphology representing implications of cancerous tissue. After signing informed consent and reviewing device lab,eling as well as determining eligibility , the subject will then have the band(s) placed on the skin tag(s) by the healthcare professional.

Once the band has been placed, the Investigator will examine the skin tag, complete study documentation, and answer any questions or concerns the subject has regarding the device or procedure. A small adhesive bandage will be placed over each treated skin tag immediately following banding. The subject will then review trial diary instructions, including but not limited to the documentation of all observable characteristics regarding the banded skin tag(s). The subject will complete their first eDiary at the visit including photo upload(s) of the banded skin tags. They will continue eDiary completion every evening starting at Day 1 through Day 20. This diary is electronic (eDiary) and accessed through the CRO's secure website. All subjects must be able to access the eDiary via smartphone to participate in the study, as defined in the informed consent. per day for eDiary completion, up to a maximum of \$200.

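### The 30–70 subjects per arm in section 6.2.1 conflicts with the 50–100 per arm stated elsewhere, and below 50 the two-tag cap rules out 100 tags per arm; the 5.5% precision is also wrong

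*Protocol*

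**What the plan says.** The protocol gives two different subject ranges for the same tag target.

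- **Section 6.2.1, near the start:** "The study cohort target is between 30 and 70 subjects per arm". The parenthesis that follows explains the range: "depending on how many skin tags each subject presents for treatment), as determined by the power analysis".
- **Section 6.1, arm tables:** "Subjects will have up to two (2) tags treated, therefore, 50–100 subjects are anticipated for this arm". The same range stands for both arms, in both the Version 1 and the Version 2 table.
- **Section 6.2.1, after the re-enrolment paragraph:** "It is anticipated that between 100 and 200 subjects will be required to treat a total of 200 skin tags". The upper end is explained there: "If the study is completed with subjects only having one skin tag treated, then the study would need to recruit 200 subjects". The lower end, 100 subjects, is the case in which everyone has two tags treated.

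The tag target and the cap do not vary. Section 6.1 states that "the number of tags for intention to treat (ITT) in each arm is 100 for a study total of 200 tags", and section 6.2.1 states "A maximum of two skin tags per subject may be chosen for treatment"; section 6.1 repeats the cap.

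On precision, section 6.1 says that at 60% removal "a study powered with 200 treated tags will have a 95% confidence interval of 5.5" per cent, and repeats the 5.5% figure at the end of its last paragraph on sample size. Section 14, Table 1, prints .54 to .66 for 60% and 200. The summary of changes records that the planning rate was 80% in Version 1 and is 60% in Version 2.

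**The concern.** A subject range and a tag target in the same section should be convertible into each other through the number of tags per subject. Here the lower part of the range cannot be converted at all, because the cap stops subjects from contributing enough tags. The remark that the range depends on tags per subject does not rescue it. The range is also attributed to an analysis that, as shown, contains no such number.

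The study calls itself pivotal. A team that recruited to the low end of the stated target could report the target as met with 60 subjects, who can supply at most 120 of the 200 tags. Separately, the protocol promises a tighter interval for the 200 tags than they can give at the planning rate now in force.

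**Working it through.** **Inputs.** Tags required: 100 per arm, 200 in total (section 6.1). Tags per subject: one or two (sections 6.1 and 6.2.1). Challenged range: 30–70 per arm (6.2.1). Competing ranges: 50–100 per arm (6.1) and 100–200 in total (6.2.1). Planning rate: 60% (6.1).

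**1. The protocol's other range reproduces.** Subjects per arm = tags per arm / tags per subject.

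- All with two tags: 100/2 = 50
- All with one tag: 100/1 = 100
- Both arms: 2 × 50 = 100 and 2 × 100 = 200

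These are exactly the 50–100 and 100–200 that the protocol states.

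**2. The 30–70 range does not.** With *s* subjects in an arm, the maximum is 2*s* tags. The mean needed for 100 tags is 100/*s*, and the share of subjects who must have two tags is (100 − *s*)/*s*.

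| Subjects per arm | Maximum tags | Mean tags needed | Share needing two tags |
|---|---|---|---|
| 30 | 60 | 3.33 | impossible |
| 49 | 98 | 2.04 | impossible |
| 50 | 100 | 2.00 | 100% |
| 60 | 120 | 1.67 | 67% |
| 70 | 140 | 1.43 | 43% (30 of 70) |

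Every value from 30 to 49 falls short. At the upper end, the all-one-tag case that section 6.2.1 allows for needs 100 per arm, so 70 would leave an arm 30 tags short. In total, 30–70 per arm means 60–140 subjects, which overlaps 100–200 only from 100 to 140.

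**3. The attribution.** Section 14 lists sample sizes from 25 to 200 in steps of 25. Neither 30 nor 70 is among them, and the section gives no number of subjects or of tags per subject. Section 6.1 says the analysis led to 200 tags.

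**4. The precision.** Normal-approximation half-width = 1.96 × √(p(1 − p)/n), treating tags as independent.

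- p = 0.60, n = 200: 1.96 × √(0.24/200) = 0.0679, or 6.8 points; interval .532 to .668
- Exact binomial, 120 of 200: about .529 to .668
- Table 1 cell: (.66 − .54)/2 = .06, or 6 points
- p = 0.80, n = 200: 1.96 × √(0.16/200) = 0.0554, or 5.5 points

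Both methods round to .53 to .67 at 60%. Section 6.1 (5.5) and Table 1 (6) therefore disagree with each other, and both are too narrow. The 5.5 matches the 80% rate of Version 1.

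**5. Other cells of Table 1.**

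- 65% and 200: printed .59 to .71; normal .584 to .716, exact .580 to .716, so .58 to .72
- 60% and 25: printed .42 to .78; normal .41 to .79, exact .39 to .79
- 70% and 25: printed .50 to .90; normal .52 to .88. An exact interval needs a whole count: 17 of 25 gives .47 to .85 and 18 of 25 gives .51 to .88. None matches.

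Section 14 also names the normal approximation in its specification and the exact binomial method in the table footnote.

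**6. Illustration of clustering.** If every subject contributed two tags, the variance would be multiplied by 1 + ICC. At assumed within-subject correlations of 0.1, 0.3 and 0.5, the 6.8 points become 7.1, 7.7 and 8.3. The protocol gives neither the correlation nor the share with two tags, and there is no inflation if each subject has one tag.

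**The case against.** The strongest objection is that little depends on the 30–70 sentence. The tag target is explicit and repeated, recruitment can simply run until 200 tags are treated, and the same section goes on to derive 100–200 subjects. No analysis, estimand or safety procedure uses 30–70, and no success criterion is tied to the width of the interval. All of this stands and limits the consequence, but it does not make the sentence right.

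The upper end deserves care. Seventy per arm is feasible if 43% of subjects have two tags, and section 6.1 says patients typically have one to five treatable tags. The two ranges overlap at 50–70, and at 49 subjects the gap is only 2 tags against a total that the figure captions give as approximate. That is fair: only 30–49 is strictly impossible. An approximate total may excuse 98 tags in an arm, but it cannot excuse 60.

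One might read 30–70 as a recruitment top-up under Version 2. No text says so, and the Version 2 table itself repeats 50–100 subjects and 100 tags per arm.

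The precision figure is a separate error with its own cause, and the 80% origin is inferred from a numerical match, not stated. Both points are right. It belongs here because it concerns the same 200 tags and the same power analysis. The handling of paired tags is properly a matter for the SAP, so the clustering figures carry no weight in the conclusion.

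**Conclusion.** The point holds: the figures are wrong as written. The 30–70 range contradicts the protocol's own 50–100 per arm and 100–200 in total, and it is not found in the power analysis to which it is credited. With the cap of two tags, 30–49 subjects yield at most 60–98 of the 100 tags per arm. The range of 50–70 works only if between 100% and 43% of subjects have two tags.

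The precision at 60% with 200 tags is 6.8 points, not the 5.5 of section 6.1 or the 6 implied by Table 1. This reads 5.5% as a half-width and assumes independent tags; positive correlation within subjects would widen it.

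The subject-count result rests only on the stated tag target and the cap. No recruitment shortfall has been shown and no decision rule changes. It should be corrected because it is a sample-size statement in a pivotal protocol and the correction costs almost nothing.

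**What to change.** - **Section 6.2.1:** replace 30–70 with 50–100 subjects per arm (100–200 in total). Attribute it to 100 tags per arm at one or two tags per subject, not to the power analysis.
- **Section 6.1:** in both places, replace 5.5% with a 95% half-width of about 6.8 points at 60% with 200 tags. Note that this assumes independent tags and is wider if two tags from one subject are positively correlated.
- **Section 14:** name one interval method, then recompute the whole of Table 1. At least the 60% and 200 cell becomes .53 to .67 and the 65% and 200 cell becomes .58 to .72; the 25-tag cells at 60% and 70% also need correction.

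The method for the final interval and the handling of re-enrolled participants can stay with the SAP.

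The cost is corrected wording in two sections and a recalculated table. The stated precision becomes less favourable. No additional tags and no change of design are needed.

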14. BIOSTATISTICIAN POWER ANALYSIS

Confidence intervals were calculated based on the following specifications:

1. Endpoint: Skin Tag Removal

2. Observed percentage = 60%, 65%, or 70%

3. Sample Size: 25, 50, 75, 100, 125, 150, 175, or 200

4. Normal approximation 95% Cls

The confidence intervals are presented in Table 1.

Table 1: Confidence Intervals for Skin Tag Removal

Sample size	95% Confidence intervals for selected observed success rates*				
	60%	65%	70%		
25	.42 to .78	.47 to .83	.50 to .90		
50	.45 to .75	.51 to .79	.57 to .83		
75	.48 to .72	.54 to .76	.59 to .81		
100	.50 to .70	.55 to .75	.60 to .80		
125	.51 to .69	.56 to .74	.61 to .79		
150	.52 to .68	.57 to .73	.62 to .78		
175	.53 to .67	.58 to .72	.63 to .77		
200	.54 to .66	.59 to .71	.64 to .76		

^{*}Using Binomial exact method

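### The planned precision counts 200 tags as 200 independent observations, although as few as 100 people may supply them

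*Protocol*

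**What the plan says.** Section 6.1 sets out the planning conditions: "The observed percentage of successful removal is 60" per cent, and "A 95% Confidence Interval (CI) was used to determine the number of subjects necessary for participation". It concludes that "a study powered with 200 treated tags will have a 95% confidence interval of 5.5" per cent. After capping treatment at two tags per person and setting 100 tags per arm, it adds: "This approach will ensure that the study has been powered to a 95% confidence interval of 5.5" per cent.

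Section 6.2.1 repeats the cap ("A maximum of two skin tags per subject may be chosen for treatment") and, for people with two tags, requires that "both skin tags must be treated in the same arm" and that the tags lie at different body locations. It says 200 subjects are needed if each has one tag, and then: "If each subject had two skin tags treated, only 100 subjects would need to be recruited". It expects a total between these two figures. The same section also gives a cohort target of 30 to 70 subjects per arm.

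Section 14 lists its method as "Normal approximation 95% Cls", while the footnote to Table 1 names the exact binomial method. Rows are indexed by sample size only. At 200 and 60% the entry is .54 to .66. No within-person correlation or design effect appears in any of these places.

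**The concern.** Both methods named in section 14 assume independent observations. Two tags on one person share that person's skin and general health. The same person carries out the diary, photographs and bandage changes for both (sections 6.2.1 and 6.2.3). Withdrawal also acts on the participant: under sections 6.2.3 and 11.2, someone who does not arrange rebanding after a detachment may be withdrawn, so a lost band on one tag can end follow-up of the other. Positive correlation between paired tags is therefore plausible. If it is present, 100 people with two tags carry less information than 200 people with one, and the equivalence in section 6.2.1 fails.

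The precision statement is the only justification given for the sample size of a study that section 6.1 calls pivotal. A reader would take from it a sharper estimate of the removal rate than the design can deliver.

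**Working it through.** **Inputs.** From section 6.1: 200 tags, success rate p = 0.60, 95% confidence (taken as two-sided, z = 1.96), stated half-width 5.5 points. From section 6.2.1: one or two tags per person, 100 to 200 people. Assumed, because the documents give none: within-person correlation ρ of 0.2 to 0.5.

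**Step 1: the plan's own figure.** Under independence the half-width is 1.96 × √(0.60 × 0.40 / 200) = 6.8 points, or 0.532 to 0.668. The exact binomial interval is 0.529 to 0.668. So 5.5 does not reproduce at 60%. It does reproduce at 80%: 1.96 × √(0.80 × 0.20 / 200) = 5.54 points. The Table 1 entry of .54 to .66 is also slightly narrower than either method gives. This is a separate error, and the comparisons below start from the correct independent value of 6.8.

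**Step 2: allowance for pairs.** With n subjects supplying 200 tags at one or two each, the number of pairs is 200 − n, and the share of tags in pairs is f = 2(200 − n)/200. Each pair adds a covariance term, so the variance of the observed rate is multiplied by 1 + fρ:

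half-width = 1.96 × √(0.24/200 × (1 + fρ))

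| Subjects | Pairs | f | Half-width, ρ = 0.2 | Half-width, ρ = 0.5 |
|---|---|---|---|---|
| 200 | 0 | 0 | 6.8 | 6.8 |
| 150 | 50 | 0.5 | 7.1 | 7.6 |
| 140 | 60 | 0.6 | 7.2 | 7.7 |
| 100 | 100 | 1 | 7.4 | 8.3 |

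With all tags paired, the effective number of tags is 200/1.2 = 167 to 200/1.5 = 133. The mathematical limit, ρ = 1 with 100 subjects, is 9.6 points. At ρ = 0 pairing costs nothing.

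**Step 3: how much pairing to expect.** The 30 to 70 per arm in section 6.2.1 means 60 to 140 subjects in all. At 140, reaching 200 tags needs at least 60 people with two tags, which is the f = 0.6 row. At 60 subjects no more than 120 tags are possible, so this target cannot be squared with 200 tags, nor with the 100 to 200 subjects given later in the same section.

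**Step 4: coverage, only if an unadjusted interval were reported.** Coverage is about 2Φ(1.96/√(1 + fρ)) − 1. With half the tags paired (factor 1.10 to 1.25) it is about 94% to 92%. With all paired (1.2 to 1.5) it is about 93% to 89%.

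**The case against.** The strongest reply is that section 14 is a planning table. Nothing in the protocol fixes how the final removal rate will be analysed, and a statistical analysis plan that is not shown may well handle two tags per person. That stands. A reader might infer that the reported interval will fall short of 95% coverage, or that per-arm and subgroup intervals share the fault. The documents do not support this: section 6.2.6.1 lists subgroups without any interval, and the coverage figures above are conditional on an unadjusted method. But no later analysis can make the planning statements in 6.1 and 6.2.1 correct.

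Some reasons for correlation are also weaker than they look. Local friction is partly separated, since the tags must be at different locations and only one of two may be in the axilla. Size class and band size are constant under protocol version 2. A shared device version matters only for the combined rate, and only if the arms differ. An operator treats many subjects, so that is not a within-person factor. What remains is the person, compliance and participant-level withdrawal. That makes positive correlation plausible but does not establish it.

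It is also fair to say that section 6.1 does not expressly promise the same precision for every mix of single and paired tags. That follows from reading it together with 6.2.1 and with a table that has no term for pairing.

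Lastly, the effect is modest, and the protocol sets no hypothesis test or lower-bound criterion that it would overturn. This bears on the size of the problem and does not make the statement right.

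**Conclusion.** The point holds as a fault in the stated planning precision. At 60% removal and 200 tags, and on the assumption that ρ lies between 0.2 and 0.5, pairing adds 0.3 to 0.8 points to the half-width with 150 subjects and 0.6 to 1.5 points with 100, against 6.8 under independence. Against the stated 5.5, about 1.3 points of the shortfall come from the separate arithmetic error and the rest from pairing, so correcting the arithmetic alone would still leave the figure too narrow for paired tags.

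The size rests on an assumed correlation and on how many subjects bring two tags, and the protocol fixes neither. A reader might also conclude that the trial is too small or its estimate biased. Neither follows: under this variance calculation pairing changes the uncertainty around the removal rate, not its expected value, and the protocol sets no criterion that would demand more subjects.

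**What to change.** In sections 6.1, 6.2.1 and 14:

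- State that precision depends on the number of subjects as well as tags. Give the half-width at both ends of the subject range with the assumed correlation, for example 6.8 points with 200 subjects and 7.4 to 8.3 with 100 at ρ of 0.2 to 0.5. Drop the implied equivalence of 100 and 200 subjects.
- Reconcile the 30 to 70 subjects per arm with the total of 100 to 200, and take the range for the precision statement from the reconciled figure.
- Say that the reported 95% interval for the removal rate will account for clustering of tags within subject, for example by robust standard errors clustered on subject. The same applies per arm or subgroup if intervals are given there. Details can sit in the statistical analysis plan.
- Because section 6.2.1 allows earlier participants to re-enrol with a different tag, count a re-enrolled person as one cluster if data from both protocol versions are pooled. Such a person could contribute more than two tags, which the pair formula above does not cover.

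The cost is wording in three sections and one sentence on the analysis. No extra enrolment is needed. The downside is a slightly less favourable stated precision.
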